11.1 Assessment of pregnancy outcome

According to the following information provided (date of last menstrual period, date of ella® intake, associated risks factors), the DMB will review all pregnancy outcomes and determine for each pregnancy complication whether it could be linked to ella® intake.

11.2 DMB assessment

Following data review, the DMB will prepare a synopsis report stating that it performed a review and giving conclusions as follows:

Conclusions on the case evaluated:

1. *There is no relationship between ella® intake and the outcome observed.*

2. *The relationship between ella® intake and the outcome observed is unknown.*
3. *It is unlikely that the outcome reported is due to ella® intake.*
4. *It is possible that the outcome reported is due to ella® intake.*

For any of the conclusions, the DMB chair will provide a copy of the written synopsis including the conclusions made during the meetings as well as supplementary comments as applicable to HRA Pharma within 15 days after the DMB meeting.

11.3 DMB working procedures

Prior to the first review, the sponsor will provide the DMB with written standard operating procedures describing the list of members, their CVs, the frequency of review, the list of data to be reviewed, the list of conclusions applicable to evaluated cases and the list of records to be archived.

12 ETHICAL AND LEGAL ASPECTS

12.1 Women information and informed consent

Women must consent in writing (hand-writing or electronic signature) prior to start completing the on-line questionnaire, and after the nature, scope and information that should be collected have been explained in a form understandable to them.

In the USA, the woman must consent in writing (hand-writing or electronic signature) after having read the ICF and a copy (paper copy or electronic record) of the signed informed consent should be retained by the participant woman. Informed Consent Form (ICF) contains all required items and HRA Pharma requirements (see Annex 2).

When the questionnaire will be completed by the HCP, HCP will download the Informed Consent form from the website and print it to enable the woman to sign and date the ICF. Signing and dating the IFC will trigger her enrolment in the study and a copy of the written ICF will be given to the woman.

For women completing the questionnaire online, in the absence of the HCP, they will have to read the ICF, acknowledge they have read and understood it by ticking the appropriate box in the questionnaire and insert their electronic signature. Acknowledging and signing electronically this form will enable the generation of a printable version of the consent and trigger her enrolment in the study. Signed ICF will have to be saved or printed-out and kept by the woman.

In all cases, the system will not allow for any data collection for the observational study if no valid electronic/or hand writing signature has been obtained from the woman and a printed version generated to allow copy retention by the woman.

12.2 Confidentiality and data protection

Women's names or e-mail details will not be supplied to the sponsor. Only the women's initials (first characters of first name/first 3 characters of last name) and age will be recorded in the reporting questionnaires, and if the woman's name appears on any other document (e.g., pathologist report), it must be obliterated before a copy of the document is supplied to the sponsor. All data (initials age and the e-mail address if the woman agrees to provide it) will allow the HPC/referent physician to identify correctly the women during the contacts with HRA Pharma.

Study findings stored on a computer will be stored in accordance with local data protection laws. As per European directive 95/46/EC requirements and Health Insurance Portability and Accountability Act (HIPAA) of 1996 Privacy Rule on data protection, women and HCP/referent physician will be informed of their right to access and amend the information collected by the Sponsor in the framework of this observational study. If a woman states such a request, the HCP/referent physician should promptly inform HRA Pharma.

12.3 Observational study approval

Before the start of the study in the USA, the study protocol will be submitted to FDA within the sponsor IND application in accordance with HRA Pharma's post-marketing commitment, and submitted to Institutional Review Board (IRB) for approval.

Before the first woman is enrolled in the study, all ethical and regulatory requirements must be met.

The authorities and institutions will be informed of all subsequent protocol amendments, in accordance with local regulations.

12.4 Ongoing information for IRB

If required by legislation or the IRB, HRA Pharma must verify that the following is submitted to the IRB:

- Information on suspected Serious and Unexpected Adverse Drug Reactions as soon as possible
- Periodic reports on the progress of the study and safety reports (at least annually).

13 MONITORING

No routine on site monitoring activity will be performed in the framework of this observational study. The only communication which may occur will be done by the sponsor's drug safety department in case of safety queries on the pregnancy outcomes, including in person visit.

14 DOCUMENTATION AND USE OF STUDY FINDINGS

14.1 Documentation of study findings

The reporting forms will be completed electronically either by the HCP or directly by the woman.

The HCP should complete forms as soon as possible after the pregnancy or its outcome is known.

In case partial information was collected (outcome not known at the time of the questionnaire completion by the HCP) and to ensure that the information on pregnancy course and outcome is correctly received, the HCP will be contacted by the Sponsor or its representative until known pregnancy outcome is obtained, according to the following schedule:

1. First contact at the time of initial declaration receipt
HCP will be reminded that they must complete information on pregnancy outcome
2. Second contact at approximately 20 weeks of woman's pregnancy

- To collect potential information on outcome, if no information was received in the meantime
3. Third contact at the scheduled delivery date
If the pregnancy outcome was not known at the second contact and no information was received in the meantime
 4. Fourth contact 3 months after the date scheduled for delivery
If no information was available at the third contact and no information was received in the meantime
 5. In case of live birth (except for neonate death), HCP/referent physician or the woman (wherever applicable) will be contacted by the Sponsor's drug safety department for safety follow up 4 months after the delivery date.

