8.3 Participant follow-up

Reporters (HCP or women) will be asked to carefully keep either their user ID and password or the unique patient number they received.

Reporters, mainly the HCP can be contacted by the Sponsor's drug safety department to obtain medical follow-up information on women included in the study or on baby(ies)'s health 4 months after the delivery date (for live births only).

However, as stated earlier, if the reporter is a woman who did not provide contact details of an HCP the system will generate an e-mail to the woman to request further information. Note that the woman email address will be kept blinded to the sponsor.

Additionally, each HCP having enrolled a woman before the pregnancy outcome was known will be contacted by the Sponsor's drug safety department at 20 weeks of the pregnancy and at the scheduled delivery date and will be asked to complete the online questionnaire accessible on the website.

This contact will be done via e-mail within 15 days after the presumed date of delivery. If no answer is received within 30 days, the HCP will be contacted again twice with 1 month interval.

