8.4 Methods of data collection

Online questionnaires for data collection will be available on a dedicated and secured website. Once submitted, these questionnaires will be received by the Sponsor's drug safety department.

Specific questionnaires may be completed on-line either by the HCP or directly by the woman at any time from pregnancy diagnosis up to known pregnancy outcome.

There will be a specific on-line questionnaire to be completed by the HCP where data on pregnancy diagnosis and exposure to ella® will first be collected. Once the pregnancy outcome is known, the HCP will be requested to complete the rest of the questionnaire.

For live birth only (except for neonatal death), HCP will be requested to complete a follow-up questionnaire 4 months after the delivery date (**4 month Follow-Up HCP Form**).

When completed directly by the woman, the woman will have to complete a simplified questionnaire where data on pregnancy diagnosis, exposure to ella®, and if known at the time of the questionnaire completion, the pregnancy outcome.

For live birth only (except for neonatal death), the woman will be encouraged to fill in a 4-month Follow-Up Form around 4 months after the delivery date (**4 month Follow-Up Woman Form**).

The on-line questionnaires together with instructions will be available in English for the HCP and in both English and Spanish for the woman.

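### Complications of pregnancy loss are a secondary objective, but the protocol sets no observation period after a loss and schedules no contact once a loss has been reported

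*Protocol*

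**What the plan says.** **What is to be estimated.** Section 2.2 makes complications of pregnancy loss a secondary objective. Section 8.1 asks for vaginal bleeding, curettage and infection for every loss. Section 9.2.2.3 singles these complications out, especially heavy or prolonged bleeding. It plans descriptive statistics for bleeding duration, the incidence of bleeding that the HCP judges excessive, and the incidence of maternal complications. Both incidences are divided by the number of losses.

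**When data are collected.** Section 14.1: "The HCP should complete forms as soon as possible after the pregnancy or its outcome is known". Section 8.4 has questionnaires completed "at any time from pregnancy diagnosis up to known pregnancy outcome". In the study schedule, the row for maternal and fetal complications has its last mark in the end-of-pregnancy column.

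**Later contacts.** Section 14.1 introduces its contact list with "In case partial information was collected (outcome not known at the time of the questionnaire completion by the HCP" and runs it until the outcome has been obtained. The second contact, at about 20 weeks, is "To collect potential information on outcome, if no information was received in the meantime". The third, at the due date, applies "If the pregnancy outcome was not known at the second contact and no information was received in the meantime". Section 8.3 has a contact rule of its own, which covers "each HCP having enrolled a woman before the pregnancy outcome was known". Under that rule such a reporter, in the protocol's words, "will be contacted by the Sponsor's drug safety department at 20 weeks of the pregnancy and at the scheduled delivery date"; the purpose is to have the web form filled in.

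**Fixed follow-up after the outcome.** Section 8.4: "For live birth only (except for neonatal death), HCP will be requested to complete a follow-up questionnaire 4 months after the delivery date". The study schedule and Section 14.1 likewise tie the 4-month follow-up to live birth. No section gives a corresponding period for losses.

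**The concern.** A duration and a cumulative incidence both need a stated period of observation. Bleeding can continue after a loss, and curettage or infection can follow it. If the form is submitted within days and nobody is scheduled to ask again, the record shows the state at submission, not the final state. Two women with the same course can then contribute different data because one reporter was quicker. Every loss still counts in the denominator.

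This is a data-collection rule and so belongs in the protocol. An analysis plan can say how to treat bleeding that was ongoing at the last report, but it cannot recover a curettage or infection that was never asked about. At stake are the loss-complication results of Section 9.2.2.3 only.

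**Working it through.** No stated figure is in dispute. The 400 pregnancies rest on Table 1, whose 398 (3% versus 6%) and 392 (1% versus 3%) reproduce with a continuity-corrected two-proportion formula: two-sided 0.05, 80% power, ratio 1:10. The point does not depend on them. The check is mainly a comparison of sections.

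**1. Follow one case through the text.** An HCP enrols a woman early in pregnancy. She loses the pregnancy at week 8, and the HCP submits the outcome form a few days later, as Section 14.1 asks.
- 14.1, first contact: a reminder to supply the outcome, made when the initial declaration is received. It is not tied to the loss.
- 14.1, second, third and fourth contacts (about 20 weeks, due date, 3 months after the due date): conditional on information not having been received. It has been, so none applies.
- 14.1, fifth contact (4 months after delivery): live births only.
- 8.3, contacts at 20 weeks and the due date: for HCPs who enrolled before the outcome was known, to get the questionnaire completed. It is already complete.

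Result: no scheduled contact after the report.

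**2. The self-enrolled woman.** Section 8.2.2.2 lets her reopen her file at any time. Section 8.3 has the system e-mail a woman who gave no HCP details. Neither is dated to the loss.

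**3. Other routes.** Section 7 (pharmacovigilance may ask for more), Section 8.3 (drug safety can contact reporters), Section 10 (expedited reporting), Section 11 (board review) and Section 13 (safety queries) are each optional, untimed, or a use of data already received. None sets a period after a loss.

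**4. Scale only.** Inputs: the 20% baseline given for miscarriage in Section 9.1, and 400 pregnancies.
- Expected spontaneous losses: 0.20 × 400 = 80.
- Effect of one missed complication: 1/80 = 1.25 percentage points, less once ectopic and induced losses enter the denominator.
- For an assumed 8 complications in 80 (10%), the exact 95% interval is 4.4% to 18.8%. Missing two would give 6/80 = 7.5%, well inside it.

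The 400 are a pooled total (Section 9.2.1), so not all of the 80 would come from this study.

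**5. A separate mismatch between the two sections.** This concerns contacts after the due date when there has been no answer.
- Section 8.3: e-mail within 15 days of the due date, then two repeats a month apart if there is no reply in 30 days. If the first repeat falls at the end of the 30 days, the last contact is 60 to 15 + 30 + 30 = 75 days after the due date. If both months are counted after the 30-day wait, it is at most 15 + 30 + 60 = 105 days.
- Section 14.1: one contact at 3 months, about day 91.

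The text does not say which rule governs.

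**The case against.** **Form timing is not an observation cut-off.** Asking for prompt completion does not bar later updates, the end-of-pregnancy mark is only a schedule column, and Section 8.1 gives no end date for loss complications. This is fair: the protocol does not forbid later data. But it does not request them either, and an open-ended permission is not a common window.

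**Case-level safeguards exist.** Fetal death and spontaneous abortion are among the expedited reports, drug safety may query outcomes and even visit, and an independent board reviews every reported pregnancy. These make it likely that some cases are followed further. They are untimed and can differ from case to case, so they do not define an incidence. Section 10 also does not list ectopic and induced losses.

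**The forms are not shown.** They may ask for bleeding start and stop dates or ongoing status. That would help the analyst recognise truncation, but it would not capture a complication that arises after submission.

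**A reader might infer that 8.3 and 14.1 conflict on the 20-week and due-date contacts,** because 8.3 states no condition and 14.1 does. The text does not support this. Section 8.3 is limited to enrolment before the outcome was known and asks for the questionnaire to be completed, so it reads naturally as pursuit of a missing outcome, and 14.1 spells out when that stops. For the same reason, intervals from a loss to the 20-week or due-date contact do not measure the gap. Those contacts obtain a first report of an unreported loss and do not revisit one already reported.

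**The benefit is limited.** This stands in part. The objective is descriptive, a few missed cases lie within sampling error, and Section 1 notes that US family planning clinics typically do not follow women once pregnant, so HCP replies may be few.

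**Conclusion.** The point holds as a gap in data collection. The protocol commits to bleeding duration and per-loss complication incidences but sets no observation period after a loss and schedules no contact after a reported loss. A prompt report can therefore miss or truncate complications.

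An early form can only undercount or shorten what it records. The size of this across the study is unknown, because the protocol gives neither the delay from loss to report nor the timing of complications. The 80 losses and 1.25 points are a scale, resting on the 20% baseline and on all 400 pregnancies. They are not an estimate of bias. A reader might infer that the planned incidences are shown to be biased; the documents do not support that.

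The primary outcomes and the sample size are unaffected. Priority is minor to moderate. The reason to act is that the data cannot be recovered later and the request is cheap.

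**What to change.** **Sections 14.1 and 8.3.** Add one e-mail request, through the existing routes, at a fixed time after a reported loss (for example about 6 weeks; this is a proposal, for the sponsor to set). It goes to the HCP, or to the woman if she gave no HCP details. It asks the reporter to confirm or update bleeding (start, stop or ongoing), curettage and infection. If the loss is first reported after that time, the first report serves.

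**Section 9.2.2.3.** State this window for losses collected prospectively in ellipse II only. Present pooled past-trial and spontaneous cases separately, or flag them as having no fixed window, because the e-mail cannot reach them. Treatment of bleeding still ongoing at last report can be left to the SAP.

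**While these sections are open,** settle the contacts after the due date with one rule in place of the two now in 8.3 and 14.1.

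**Cost.** One automated e-mail, a few sentences, and a minor amendment with IRB submission and notice to authorities (Section 12.3). Expect a small reporter burden and some non-response. Excessive bleeding is defined by HCP judgement, so a woman's own reply can inform duration, curettage and infection but cannot supply that endpoint.

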14.2 Use of study findings

The sponsor has full ownership of the original data completed as part of the study.

The HCP agrees that the results of the study may be used for the purposes of national and international publications, and information for medical and pharmaceutical professionals.

The sponsor will prepare a final report on the study and will communicate a summary of key findings to all HCP.

The sponsor intends to publish the results of the study within 24 months after completion of the study. If the sponsor publishes the results of the study during such 24-month period, the principal investigator, on behalf of the ella® observational study group, may elect to serve as co-authors of such publications, and following publication, will be permitted to present the results of such publications in symposia.

A progress report of the study will be included in ella® PSUR and DSUR sent to Health Authorities every year.

Additionally, a descriptive analysis of the data collected will be provided annually in the PSUR submitted yearly.

15 STUDY DURATION AND DATES

Recruitment will be done through website access. Implementation of the website is planned for the second quarter 2014. Website will be in place during the whole course of the study.

ANNEX 1: REFERENCES AND STATISTICAL TABLES

References:

Table 1. Sample size calculations for comparison of adverse pregnancy outcomes for pregnancies exposed to ella® versus those unexposed (or in the general population)

Pregnancies	Proportion of adverse outcomes in the unexposed population (%)											
	20,0	20,0	10,0	10,0	5,0	5,0	3,0	1,0	1,0	0,1	0,1	0,05
	Proportion of adverse outcomes in the exposed population (%)											
Risk Ratio	30,0	40,0	15,0	20,0	7,5	10,0	6,0	2,0	3,0	0,3	1,0	0,5
	1,5	2,0	1,5	2,0	1,5	2,0	2,0	2,0	3,0	3,0	10,0	10,0
Sample sizes												
Ella exposed	164	46	375	108	798	232	398	1225	392	3978	479	959
Unexposed / general population	1640	460	3750	1080	7980	2320	3980	12250	3920	39780	4790	9590

*Notes: Event rates / proportions would be comparable for an unexposed population vs. the corresponding source population as essentially all would be unexposed to ella®. All calculations assume a type-I (alpha) error rate of 0.05, two-sided tests and a ratio of exposed to unexposed group of 1:10. Higher ratios (e.g., 1:6 or 1:4) would require somewhat higher sample sizes for the exposed group but the difference would be relatively small as the main determinant of study power will be the number of exposed pregnancies. Furthermore, notwithstanding the caveats for selection of reference population(s) or a comparison group(s), various sources of data may be found for large numbers of (essentially all) unexposed pregnancies for different adverse pregnancy outcomes (e.g., population-based registries for congenital anomalies).

